2.2 Study Rationale

Interventions: The wake therapy and light interventions proposed in this application are based on our previous studies in PMDD³⁶⁻³⁹ and key published experiments by other investigators that indicate that the combined interventions are efficacious in other mood disorders after one week of treatment and maintained at 9-months follow-up.¹⁷⁻³¹ To provide optimal timing of interventions, we will administer wake therapy in the early-night vs. late-night and light pulses in the AM vs. PM at selected times in relation to sleep (within 30 min of waking and 90 min before sleep onset, respectively). These times were selected to examine phase-advance and phase-delay responses without disrupting sleep. Successful light treatment is associated with a phase-shift of the melatonin rhythm as noted by Epperson et al.⁴⁰ in a randomized trial of bright light therapy for antepartum depression and by Terman et al.⁴¹ in winter depression. In this proposal focusing on mood effects, we will administer 7 days of AM or PM light after wake and before sleep, respectively, for 60 min using a light-emitting diode (LED) device. The advantage of LEDs over conventional light boxes (fluorescent or incandescent) is that LEDs can be selected to emit light with energy concentrated at wavelengths of 450-480nm to which the human circadian system is most sensitive.⁴²⁻⁴⁴ Thus LEDs are not only more efficient, but smaller and light-weight, further enhancing patient compliance. Clinical effects on mood generally occur within 3-4 days after the onset of treatment, and expire within 3-4 days after discontinuation of treatment.^{45, 46}

A crossover treatment design will be employed to compare LWT+AM BWL vs. EWT+PM BWL responses within the same individual. As wake interventions lose effectiveness after 1 day, and light treatment effects after 3-4 days, we anticipate minimal carry-over effects of the wake plus light interventions administered a month

apart. To further ensure no carry-over effects, there will be a month of no-intervention between the 1st and 2nd treatments. Because our previous studies clearly indicated differences between PMDD and NC subjects occurred primarily in the luteal menstrual cycle phase, we will treat during this menstrual cycle phase rather than in the follicular phase.

Melatonin measures: To make the study more clinically feasible on an outpatient basis and to reduce subject burden, instead of plasma melatonin measures requiring now expensive inpatient admissions, we will obtain two overnight collections (30+ h) of urinary 6-sulfatoxymelatonin (6-SMT) pre- and post-intervention. Since light suppresses melatonin acutely (within 30 minutes), melatonin measures will be obtained after completion of the light treatment to avoid confounding the suppressive effects with the phase-shifting effects of light. Based on previous work,^{1, 47, 48} we know melatonin profiles are stable and consistent within an individual when measured at different time points. These characteristics make melatonin one of the best markers for circadian rhythmicity in humans in non-constant routine conditions, if light is controlled appropriately. We will not use a constant routine, as it is not needed to obtain informative circadian parameters from rhythms in urinary 6-SMT, is burdensome, not clinically feasible for depressed patients in an outpatient setting, and has less potential therapeutic application. Melatonin is also a very useful marker because it is little masked by exercise, sleep, diet or stress when compared with other circadian parameters such as temperature, cortisol or activity measurements. Measuring 6-SMT in the urine has similar advantageous characteristics, and is less expensive and burdensome to patients compared with plasma measures. Moreover, the power of this method has been clearly and extensively demonstrated at UCSD by our collaborators Drs. [name], [name] and colleagues.^{49, 50}

Other biological rhythm measures such as sleep and activity may be independently regulated, but coupled. Therefore, it is informative also to measure these components of the circadian system in order to better quantify and understand the circadian response to treatment and its impact on mood and sleep.

3. STUDY DESIGN

Forty PMDD subjects will be recruited. Menstrual cycle phase will be established by measuring the mid-cycle LH surge using a urinary colorimetric assay (Clearblue® colorimetric LH assay, Princeton, New Jersey). Failure to ovulate will exclude the subject from participating that month, and the study will be postponed until a following month when ovulation can be documented.

Overall Design (see Figure 1): Month 1 consists of a screening evaluation using daily mood ratings (DMR) (see Section 6: Subject Selection). In Month 2, evaluations are continued, the Structured Clinical Interview for DSM-IV (SCID)^{51, 52} and documentation of ovulation by the LH surge (approximately menstrual cycle day 14) are performed. In the Month 2 luteal phase, PMDD subjects will collect overnight urine samples for 6-SMT and reproductive hormones (RH) (estradiol, progesterone, FSH, LH, prolactin) starting 8-9 days after the LH surge (approximately menstrual cycle days 22-23). These baseline urine sample collections are timed to coincide with post-intervention measures in months 3 and 5. Starting in Month 3, after the LH surge (luteal phase), subjects will undergo a night of LWT (sleep 21:00-01:00 h, followed by wake) vs. EWT (wake until 03:00 h followed by sleep until 07:00 h) at home. We selected the specific wake and sleep times based on our previous work in

PMDD.^{36, 37} The following day, subjects will receive the light intervention for 7 consecutive days: days 1-7 after the LH surge (approximately menstrual cycle days 15-21). We will randomize subjects to 60 min of either AM bright white light (LED of 1350 lux at 20 inches) starting within 30 minutes of their habitual wake time, or PM bright white light ending 30 min before their habitual sleep onset time. After completing seven days of light exposure, subjects again will collect 30+ hours of urine samples over 2 nights (between days 8-9 after the LH surge, approximately menstrual cycle day 22-23). The following Month 4 (Washout) will be a month of no intervention to prevent any carry-over effects from the Month 3 intervention affecting measures in Month 5. Mirroring Month 3 timing, in the luteal phase of Month 5, subjects will receive the alternate wake therapy (LWT or EWT) and light exposure (AM or PM), followed by 2 overnight collections of urinary 6-SMT and RH samples. See Fig. 1, below.

This design allows us to complete the studies at least two days before the next expected menstrual period. Measuring the circadian profile of urinary melatonin over 2 nights for 30+ h will allow us to assess phase, duration and amplitude changes of melatonin reflective of the underlying circadian pacemaker. In addition, we will assess phase-shift responses of melatonin to light in relation to other critical biological rhythm measures of sleep and activity. To document the sleep/wake cycle and exposure to light intensity and spectra, we will use the Actiwatch device (see description below).

[figure not shown]

Figure 1. Study flow: The luteinizing hormone surge (LHS) documents ovulation, c. menstrual cycle day (CD) 14. Urine samples for 6-sulphatoxy-melatonin (6-SMT) and reproductive hormones (RHs) will be collected for 30+ hours over 2 nights between days 8-9 after the LH surge (c. CD 22-23) in months 2,3,5; actigraphy will begin the day of LHS and continue until day 10 after the LHS (CD 14-24) of months 2,3,5; late wake therapy (LWT) or early wake therapy (EWT) will be administered at home on the night of the LHS; bright morning (AM) or evening (PM) light will be administered on days 1-7 after the LHS (CD 15-21) in a counterbalanced, cross-over design in months 3 and 5. Mood ratings (HRSD+BDI) will be collected as follows: Months 1 & 2 – once per week; Months 3 & 5 – LHS + 0 (Pre-

LWT/EWT), daily LHS +1 → LHS + 2 and once the evening after last treatment (LHS +7/8). Visual Analogue Scales (VAS) for depressed mood, anxiety, affective lability, irritability (Daily Mood Ratings)(core PMDD symptoms) collected daily during Months 1 & 2, and twice daily on LHS + 0 through LHS + 2 (for wake therapy effects) and daily LHS + 3 through LH + 10 (for light treatment effects) in Months 3 & 5. HRSD will be collected once during Month 4 and a once a month after Intervention 2 to monitor relapse.

Urinary Collections for 6-SMT and RH: For urine collections, subjects will measure and record the time and total volume of each urine voided over a 30-hour interval starting with the last urination before going to bed one evening and ending on the morning of the second day thereafter. Two 2 ml aliquots from each voiding will be frozen at home in duplicate using labeled and numbered vials, and later stored at -70 C in the lab until assay. Subjects will receive thorough instruction regarding accurate recording of time and volume and proper collection and storage of the aliquots associated with each sample, including hands-on experience. Subjects also will be encouraged to drink extra fluids during waking hours (~ 200 ml every 2 hours) to remain well-hydrated and to facilitate more frequent voiding. Subjects will receive an oversupply of duplicate sample vials, each with easily read numbers on the printed label which are repeated on the vial tops to ensure correct identification of each sample with the associated time and volume on the record sheet. They also will be supplied with 1000 ml plastic bottles for refrigerator storage of samples collected during awakenings at night (so that volume measurement and transfer to freezer vials can be postponed until morning). The above urine collection methods have served us well for many years.^{49, 50, 53}

Actigraphy Measures: Measures of activity and illumination using the Actiwatch Spectrum device will be obtained for 10 days in the luteal phase starting on the day of the LH surge during the 2nd month of screening evaluation and during each subsequent intervention month. The Actiwatch Spectrum, developed by Respirationics®, a subsidiary of Royal Philips Electronics, is a small device (48.5 x 36.7 x 13.8 mm and weighing 29.8 g with band) containing a piezoelectric linear accelerometer (sensitive to 0.003 g and above), log-linear photometric transducer (sensitive from <0.01 lux to >100,000 lux), 3 photon flux and irradiance color sensors in the red, green, and blue bands of visible light, a microprocessor with 2 Mbits RAM memory that allows for 36 days continuous recording of 1-minute epochs, and associated circuitry. The orientation and sensitivity of the accelerometer are optimized for highly effective sleep-wake inference from wrist activity. The illumination measurements are roughly log-linear from a range below moonlight to the brightest summer day at noon. An important innovative feature of this device is an off-the-wrist sensor, which distinguishes when the participant has removed the device for any reason. The Actiwatch Spectrum also allows us to determine spectral composition of light, which may differentially affect phase-shift, and therefore, treatment responses.⁴⁵

Sleep Interventions: Adherence to appropriate sleep and wake times during the EWT and LWT interventions will be documented by actigraphy. Compliance with wake therapy also will be monitored by having patients leave a message on an answering machine once every half-hour while awake. As they are only awake for 4 hours during wake therapy, they will make 8 calls.

Light Interventions: Subjects will sit in front of a portable (5.5" x 6.25") Litebook® Model 1.2 light box (an array of 60 cool white light-emitting diodes behind a clear

plastic screen)(The Litebook Company Ltd., Alberta Canada) with an intensity of 1,350 lux and an irradiance of 2.41×10^{-9} w/cm² at 20 in, and spectral emission peaks at 464 nm and 564 nm. Subjects will gaze at the light source for a minute every few minutes for 30 min. The distance of the subject from the light source will be calibrated individually for each light box by use of a Meterman LM631 Digital Light Meter (Meterman Test Tools, Everett, WA) to produce an intensity of 1,350 lux at 20.0 in. Ambient light intensity and spectra will be documented by the Actiwatch Spectrum. A research assistant will provide a measuring tape to ensure proper distance between light source and patient, check the Actiwatch recordings to ensure compliance, as well as the Litebook’s built-in compliance monitor recordings.

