[name]
[name]
(ph) [contact]
(fx) [contact]
[contact]

[name], B.S., Senior Research Technician

[name]
[name]
(ph) [contact] [name]
[contact]

[name], Project Assistant

[name]
[name]
(ph) [contact]
(fx) [contact]
[contact]

PARTICIPATING STUDY SITES

University of California, San Diego Medical Center in Hillcrest.
[name].
[name]
(ph) [contact]

PRÉCIS

Study Title

Alternative Treatments for Premenstrual Dysphoric Disorder

Objectives

The primary aim of this study is to examine the effects of co-administered wake therapy followed by light treatment on mood and circadian rhythms to test the hypothesis that critically timed chronotherapy improves mood by correcting phase disturbances in melatonin and sleep in women with Premenstrual Dysphoric Disorder (PMDD).

Design and Outcomes

40 women with Premenstrual Dysphoric Disorder ages 18-45 will be randomized to a cross-over design contrasting one night of Late Wake Therapy followed by 7 days of morning Bright-White Light (LWT+AM BWL) vs. one night of Early Wake Therapy followed by evening Bright-White Light (EWT+PM BWL) administered in the luteal phase of two separate menstrual cycles. Treatment will be preceded by 2 evaluation months to determine diagnosis and collect baseline mood, sleep, actigraphy and endocrine measures. To lessen the patient's burden, the 1-night EWT or LWT and the following 7-day BWL interventions will be conducted at home, given at a fixed point in each menstrual cycle, from day 1 to 7 after the mid-cycle LH surge. We anticipate that LWT+7 days of AM BWL (vs. EWT+PM BWL) will produce much greater mood benefits and larger physiological responses, than the one-time light pulses used in our earlier phase-shift studies.^{1,2}

Interventions and Duration

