Using a randomized cross-over design, in the luteal phase of their menstrual cycles, PMDD women will receive either 1) one night of LWT (sleep 21:00-01:00 h, followed by wakefulness) plus 7 days of AM BWL (light-emitting diode-LED administered for 60 minutes, starting within 30 minutes of habitual wake time) or 2) EWT (wakefulness until 03:00 h, then sleep 03:00-07:00 h) plus 7 nights of PM BWL (administered 90 minutes before habitual sleep onset, for 60 minutes). Following this first intervention, patients will undergo one washout month with no intervention. The second intervention will be completed in the luteal phase of the following month and will be the treatment opposite the one previously performed. Total study duration, including evaluations and washout, will be 5 months (see Figure 1, Section 3, for detailed study flow diagram).

Sample Size and Population

In order to achieve the targeted enrollment goal of 40 completed subjects allowing for a 20% drop-out rate, 48 PMDD women ages 18-45 will be recruited to participate in the study.

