4. SELECTION AND ENROLLMENT OF PARTICIPANTS

Subjects for these experiments over 5 years will include: Forty women with premenstrual dysphoric disorder (PMDD). As only women have menstrual cycles, only women will be sought. As women generally do not develop significant premenstrual mood symptoms until late adolescence, and the menstrual cycle may become irregular during the perimenopause, only women age 18-45 years will be studied. For these reasons, children and adolescents under the age of 18 and peri- and post-menopausal women will be excluded. All ethnic groups will be represented (Caucasian, Asian, Black, Hispanic and Other). We will focus on recruiting subjects representative of the community: approximately 54% Caucasian, 30% Hispanic, 10% Asian, 5% African American and 1% Other. The UCSD Medical Center serves a clientele in which minorities are over-represented. All subjects will be adults individually competent to execute written informed consent.

Recruitment of minority subjects: We will take pains to recruit women of color and other minorities working with the Women’s Center, the Cross Cultural center, the Lesbian, Gay, Bi-Sexual and Transgender (LGBT) Resource Center, Queer People of Color (QPOC) Center and the Native American Student Alliance on the University of California campus.

	Caucasian	Hispanic	Asian	Black	Other
Female	54%	30%	10%	5%	1%

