9.2 Sample Size and Randomization

For our primary outcome measures of mood, based on our earlier data reflecting

seven days of light exposure alone² (i.e., without the ‘priming’ effect of wake therapy), we predict the following changes in mood in PMDD subjects (N = 40) after Late Wake Therapy plus AM Light vs. Early Wake Therapy plus PM Light: A significantly greater improvement (decrease in raw score) will be detected at the p = .05 level with (a) 71% power in Hamilton Rating Scale for Depression (HRSD) Score (Mean difference 3.15±9; effect size = .324); (b) > 99% power in atypical score (Mean difference 4.45±5; effect size = .78); (c) > 99 % power in Structured Interview Guide for the Hamilton Depression Rating Scale, Seasonal Affective Disorders (SIGH-SAD) Items (Mean difference 7.0±11; effect size = .627); (d) 86% power in Beck Depression Inventory (BDI) score (Mean difference 6.30±15; effect size = .378).

For the recovery criterion of $\geq 50\%$ decrease from baseline (Chi Square analyses): (a) 97% power for HRSD score (difference in proportions: .44); (b) 70% power for atypical score (difference in proportions: .30); (c) 86% for SIGH-SAD score (difference in proportions: .325); and (d) 93% power for BDI score (difference in proportions: .40). For the remission criterion of reduction to a score of ≤ 8 (Chi Square analyses): (a) 89% power for the SIGH-SAD score; (b) 44% power for the BDI score. All tests are two-tailed.

We also performed power analyses for the primary hypotheses, incorporating the longitudinal nature of the design for the proposed Random Regression model (also known as Multilevel Models, or Growth Curve Models). Procedures describes by Hedeker et al.⁶⁹ for Random Regression Models, with the above data, was used for the proposed study to estimated needed sample size. We assume a Type-I error level (alpha-level) of 0.05, drop-out rate of 10% to 15% and an autoregressive covariance structure, with correlation between sequential assessments set at 0.45 (based on our previous data). We are confident based on our results from these two separate approaches that the proposed study will have minimum power of 80% to yield a statistically significant result for a medium effect size. Here, medium effect size is defined as a treatment difference increasing linearly from 0 at baseline to .5 SD units at the last time point. Type 1 error will be controlled by correcting the p-value per domain.

Treatment Assignment Procedures

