9.3 Definition of Populations

Forty women with DSM-IV diagnoses of premenstrual dysphoric disorder (PMDD) will be selected for the study. Before entering the study, patients will be screened using standardized questionnaires and the Structured Clinical Interview for Diagnosis (SCID), complete daily mood self-ratings for two months (required to confirm a DSM-IV diagnosis) and visit our clinic weekly for Hamilton, Beck, atypical and mania ratings to observe individual changes in symptoms over the menstrual cycle that include symptoms of anxiety, irritability, mood lability and physical discomfort. Eligibility, inclusion and exclusion criteria are listed below. All subjects with valid baseline and at least one post baseline measurement will be included in the analysis.

PMDD Subjects: Eligibility, Inclusion and Exclusion Criteria:

Inclusion criteria

- 1) Age: 18-45 years.
- 2) Women with regular ovulatory menstrual cycles 26-32 days in length (for at least the previous six months).
- 3) A history of a depressive (but not bipolar) mood disorder, but not an ongoing episode (symptom free for the last 12 months).
- 4) Patients must meet DSM-IV criteria for Premenstrual Dysphoric Disorder (that includes irritability).
- 5) Objective ratings: mean of HRSD total scores across evaluation weeks 1-8 \leq 7 for follicular phase (day 5-10 of cycle after menses); mean of total HRSD scores across evaluation weeks 1-8 \geq 14 for premenstrual (luteal) phase (6 days prior to onset of menses onward).
- 6) Subjective ratings: mean of Beck Depression Inventory total scores across evaluation weeks 1-8 $<$ 10 follicular phase; \geq 10 premenstrual (luteal) phase.
- 7) Daily ratings: minimal symptoms (mean less than 50 mm on 100mm scale) follicular phase; at least a 30% increase in mean affective symptom ratings, premenstrual (luteal) phase.

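### The plan uses forty for women recruited, women randomized and completers, with two drop-out rates; if only 40 enter, complete pairs fall to 32–36 and HRSD and BDI power drops by about 4–10 points

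*Combined protocol and SAP*

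**What the plan says.** Forty appears at several stages of the trial.

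- **Précis, Design and Outcomes** (randomized): "40 women with Premenstrual Dysphoric Disorder ages 18-45 will be randomized to a cross-over design".
- **Précis, Sample Size and Population** (completers, with a larger intake of 48): "In order to achieve the targeted enrollment goal of 40 completed subjects allowing for a 20% drop-out rate".
- **Section 3** (recruited): "Forty PMDD subjects will be recruited".
- **Section 4** (stage not stated): "Subjects for these experiments over 5 years will include: Forty women with premenstrual dysphoric disorder (PMDD".
- **Section 9.3** (stage not stated): "Forty women with DSM-IV diagnoses of premenstrual dysphoric disorder (PMDD) will be selected for the study".

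Section 9.2 prints its mood mean-difference powers for N = 40 with two-tailed tests: HRSD 71%, atypical score above 99%, SIGH-SAD above 99%, BDI 86%. It then describes a separate power analysis for the random regression model, with a "drop-out rate of 10% to 15% and an autoregressive covariance structure", and concludes that power is at least 80% for a difference reaching 0.5 SD. Sections 9.3 and 9.6 keep women with incomplete data in the analysis.

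**The concern.** Forty cannot be at once the number recruited, the number randomized and the number completing unless no one leaves, and the plan itself expects 10–20% to leave. The Précis sample-size paragraph is the only place that separates intake from completers. A coordinator working from Section 3 would have grounds to close recruitment 8 women (48 − 40) below the Précis figure.

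The number is used in running the trial. The randomization table is prepared before start-up, Section 9.4 allows stopping for difficulty with recruitment or retention, and the monitoring committee is asked in Section 10.3.2 whether goals are being met. Each needs one target. The mean-difference powers in 9.2 are printed at N = 40 with no drop-out allowance of their own, so an intake of 40 would leave fewer complete within-woman contrasts than those figures use.

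**Working it through.** **Inputs.** Entrants: 40 (Section 3; Précis design) or 48 (Précis sample size). Drop-out: 20% (Précis), 10–15% (9.2). From 9.2, two-tailed α = 0.05 and these mean differences ± SD, with printed effect sizes: HRSD 3.15 ± 9 (.324); atypical 4.45 ± 5 (.78); SIGH-SAD 7.0 ± 11 (.627); BDI 6.30 ± 15 (.378).

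**Assumption.** Section 9.2 names neither the test nor the kind of SD. I take a paired t-test and treat the SD as that of the within-woman difference. The printed effect sizes differ from mean/SD (HRSD 3.15/9 = .350; BDI 6.30/15 = .420; SIGH-SAD 7.0/11 = .636; atypical 4.45/5 = .890), so both are shown.

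**Step 1: head counts.** Completers = entrants × (1 − drop-out).

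- 40 × 0.90 = 36; 40 × 0.85 = 34; 40 × 0.80 = 32.
- 48 × 0.85 = 40.8; 48 × 0.80 = 38.4.
- Entrants needed for 40 completers at 20%: 40/0.80 = 50. At 15%: 40/0.85 = 47.1, so 48.

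The Précis figure of 48 equals 40 × 1.20. It matches a 15% drop-out rate, not the 20% beside it.

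**Step 2: the plan's own powers at 40 pairs.** Power comes from the noncentral t with n − 1 degrees of freedom and noncentrality d√n. Two-sided at n = 40, HRSD is 57.9% (d = .35) or 51.5% (.324), against 71% printed. BDI is 73.6% (.42) or 64.5% (.378), against 86%. SIGH-SAD is 97.5% or 97.2%, against above 99%. The atypical score is 99.8% or more and agrees. The HRSD and BDI figures therefore do not reproduce even with 40 full pairs. A one-sided normal approximation with mean/SD comes within 2 points (HRSD 71.5%, BDI 84.4%), but 9.2 says its tests are two-tailed.

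**Step 3: effect of attrition alone.** Same test, fewer pairs:

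| Outcome (d) | 40 | 36 | 34 | 32 |
|---|---|---|---|---|
| HRSD (.350) | 57.9% | 53.3% | 50.9% | 48.3% |
| HRSD (.324) | 51.5% | 47.2% | 45.0% | 42.7% |
| BDI (.420) | 73.6% | 68.8% | 66.2% | 63.4% |
| BDI (.378) | 64.5% | 59.7% | 57.1% | 54.5% |
| SIGH-SAD (.636) | 97.5% | 96.0% | 95.0% | 93.7% |
| SIGH-SAD (.627) | 97.2% | 95.5% | 94.4% | 93.0% |
| Atypical (.78) | 99.8% | 99.5% | 99.3% | 99.0% |

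HRSD and BDI lose about 4 to 10 points. If the printed 71% and 86% are instead taken as true at 40, they become 66/64/61% and 82/80/77%, so the loss does not depend on the starting point.

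**Step 4: the 80% statement.** A simple paired test at 0.5 SD has 83.1/80.8/78.2% power at 36/34/32 pairs. This is a rough check, not a reconstruction of the random regression calculation.

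**Step 5: response rates.** Section 9.2 prints only differences in proportions. With 32 per condition treated as independent groups, the possible base rates give HRSD 95.9–99.5% (printed 97%), atypical 67.8–92.5% (70%), SIGH-SAD 75.1–95.4% (86%) and BDI 91.2–98.8% (93%). Every printed value lies inside its range.

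**The case against.** The best defence is that forty is shorthand for the completer target. The Précis sample-size paragraph sets out both numbers, and Sections 4 and 9.3 never use the word recruited, so both could mean completers. That much stands: a reader might infer that Sections 3, 4 and 9.3 all fix recruitment at 40, but only Section 3 does. The defence fails for Section 3, which applies to 40 the same verb that the Précis applies to 48, and for the Précis design paragraph, which randomizes 40. Nor does 48 recruited shrinking to 40 randomized resolve it: the Précis applies its drop-out to reach completers. Forty-eight is not a screening count either, since Section 4.3 expects about 5% of those screened to qualify (48 × 0.05 = 2.4).

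A second defence is that 9.2 does allow for drop-out and that the planned model uses partial data. This stands for the random regression power. It also means that complete pairs are not the analysed N, so counting each drop-out as contributing nothing overstates the loss. A woman with one treatment period still supplies no within-woman treatment contrast, so some loss remains.

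A reader might also infer that the 9.2 powers as a whole fail because of attrition. The documents do not support that. The atypical score holds, the response-rate powers cannot be shown to be lost, and HRSD and BDI fall short before anyone drops out.

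**Conclusion.** The plan contradicts itself on how many women enter and on the drop-out rate. An intake of 40 would leave 32 to 36 complete pairs. Under a two-sided paired t-test, with the printed SD read as the SD of the within-woman difference, attrition alone costs HRSD and BDI at most about 4–10 points and takes SIGH-SAD from about 97% to 93–96%. The 80% statement is roughly kept at 10–15% drop-out and slips just below at 20%.

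The HRSD and BDI shortfall at 40 full pairs is a separate defect and should not be charged to attrition. The point is worth correcting because sample size and power are figures that the trial relies on, but it does not show a general failure of power.

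**What to change.** State one number recruited and randomized (or two, if they are meant to differ), one number of expected completers and one drop-out rate. Use the same figures in both Précis paragraphs and in Sections 3, 4, 9.2 and 9.3, saying in Sections 4 and 9.3 which stage the number describes.

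Make the figures agree. Copying 48 into Section 3 is not enough, because at the Précis's own 20% it yields about 38 completers. Either 48 entering at 15% gives about 40, or 48 at 20% gives about 38 and the target is restated.

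Then restate the 9.2 mean-difference powers, two-sided, at the expected number of complete pairs, and say what the printed SD is. The cost is wording in five sections and one recalculation, with no women beyond the 48 already planned.
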